#### 6.1 EFFICACY/EFFECTIVENESS OBJECTIVES

- Progression-Free Survival (PFS): PFS will be studied using Kaplan Maier survival curves, considering progression/death as the event and time to event as the interval from the start of treatment until the first date that progressive disease (PD) is observed according to RECIST criteria (Version 1.1) or until *death*. Patients who have not had an event at the time of the analysis of the study data will be censored on the date of the last available follow-up.

- Objective Response Rate (ORR): defined as the proportion of subjects who achieve complete remission (CR) or partial response (PR). Additionally, the patients with stable disease (SD) will be evaluated. The subjects will be evaluated in accordance with RECIST criteria (Version 1.1).

- Duration of response (DOR): in patients with PR or CR, it will be defined as the interval from the date the response is documented to the first date that progressive disease is observed.

\_Time to Treatment Failure (TTF), defined as the time from the start of treatment with a tyrosine kinase inhibitor to tumour progression, treatment discontinuation for any reason or death from any cause.

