7.2. Scope

The study will start at each site after the contract has been signed by all parties and all documentation and information on the procedures and objectives of the study have been received by the person appointed by the sponsor.

Recruitment will be competitive between all the participating sites (estimating between 1 and 4 patients per site) and will finish once 100 patients have been recruited.

The investigator will be guided by routine clinical practice at all times when making decisions regarding the best available treatment option for the patient.

At the Baseline Visit, patients will sign the informed consent form and their participation in the TROYA study will be recorded in their medical records.

There should be evidence of a signed and personally dated *informed consent* document indicating that the patient (or his/her legal representative) has been informed of all aspects of the study and the *patient information sheet*, with a record being made in the patient's medical records that the patient received a copy.

All patients who are about to start first-line treatment with a tyrosine kinase inhibitor and who meet all the inclusion criteria and no exclusion criterion are candidates for this study.

The information requested at all of the study visits will be recorded on the electronic CRF (Case Report Form) attached in Annex 2.

Different aspects for improving the quality of life of patients, such as drug administration time, weekly mild-moderate aerobic exercise and napping, will be evaluated. For this purpose the patient will complete this information in a diary (*Patient Diary*).

Other aspects, such as temporary treatment interruptions and dose reductions, will be recorded on the CRF at each visit.

Quality of life will be evaluated at the Baseline visit, the 3 month visit (coinciding with the first control CT according to routine clinical practice), the 6 month visit (second CT) and the 9 month visit (third CT) using the validated Spanish version of the **FACIT–Fatigue** questionnaire. Other evaluations may also be conducted using this questionnaire at any additional visits scheduled for the patient according to the site's clinical practice.

Each patient will complete the questionnaire after it has been explained by the clinician or a person appointed by the investigator (nursing staff, clinical trial coordinator).

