7.9. Limitations of the research methods

The Patient Diary will contain epidemiological data that cannot be confirmed by the Investigator, although guidelines will be provided during the initial visit to each site to standardise the collection of such data.

PFS will be evaluated by each investigator in line with routine clinical practice with no centralised evaluation.

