8.5. Interference with the physician's prescribing habits

There will be no interference with the investigator's decision on the most appropriate treatment for the patient.

This is a non-interventional study and therefore the decision to prescribe any treatment will be made prior to and independently of the patient's participation in the study; i.e. patients will receive the same medication whether they participate in the study or not according to the clinical judgement and normal clinical practice of the doctor responsible for the patient. Moreover, no additional tests are to be performed as part of the study.

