#### TREATMENT

- 1) Time when the oral treatment is taken
- 2) Tyrosine kinase inhibitor dose and treatment regimen
- 3) Number of dose changes per treatment cycle
- 4) Temporary treatment interruptions, number of interruptions per treatment cycle
- 5) Best response achieved with first-line treatment
- 6) Mean duration of treatment
- 7) Time to treatment failure
- 8) How long each patient stays on first-line treatment/no. of cycles received
- 9) Reason for discontinuing the first-line drug
- 10) Date of disease progression and/or death

Through the analysis of the collected variables the following aspects will be assessed:

- **Progression-Free Survival (PFS):** defined as the interval from the start of treatment to the date of the first documentation of objective tumour progression or death from any cause.

- **Objective Response Rate (ORR):** Defined as the proportion of subjects who achieve complete remission (CR) or partial response (PR). In addition, subjects with stable disease (SD) will also be evaluated to obtain clinical benefit along with subjects with tumour progression. Subjects will be evaluated according to RECIST 1.1.

- **Duration of response (DOR):** in patients with PR or CR, it will be defined as the interval from the date the response is documented to the first date that progressive disease is observed.

- **Safety:** The safety of the tyrosine kinase inhibitor will be evaluated describing the incidence and all grades in the event of fatigue and or hand-foot syndrome.

- **Fatigue-related quality of life of patients:** this will be measured based on the results obtained after completion of the FACIT-Fatigue questionnaire by the patient.

- **HFS-related quality of life of patients** in cases in which HFS is present with a score from 1 to 3 according to version 4 of the CTCAE (Common Terminology Criteria for Adverse Events).

- Date of disease progression and/or death.

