#### 8.2.4 **Efficacy analysis**

For the patient efficacy analysis, the following will be studied on completion of the firstline treatment or else on the date of the patient's last follow-up when the cut-off is decided:

- Number of treatment cycles received, presenting the frequency distribution of  $\dot{\mathbf{x}}$ patients according to the number of cycles of treatment with the tyrosine kinase inhibitor in first line.
  - 0 1 2
  - 0 0
  - 3 4 0

  - 5 0 6
  - 0

CT24-GSOP-SD-GL04 NI Study SAP Template; Template Version 1.0, Effective 31-Dec-2013 Page 20 of 29 o ...

- Best response rate achieved, presenting the frequency distribution of the patients based on the best response achieved with tyrosine kinase in first line.
   CR
  - $\circ$  PR
  - o PR o SD
  - 0 SD
  - o DP
- **ORR**, the absolute and relative frequency of patients who have achieved an objective response rate will be given (CR+PR).
- ✤ CBR, the absolute and relative frequency of patients who have achieved a clinical benefit rate will be given (CR+PR+SD).
- DOR, for the sub-population of patients who have achieved ORR, the time from the date of the response to the date of progression will be calculated, providing the value of the mean, standard deviation, median, range, interquartile range and 95% confidence interval.
- Time to the best response, calculated as the difference between the treatment start date and the date on which the best response is achieved. Providing the main measures of centrality and dispersion.
- Time on treatment, calculated as the difference between the treatment start date and the treatment end date or the date of the last follow-up if the patient is still on first-line at the time of the cut-off. It will be studied using the value of the mean, standard deviation, median, range, interquartile range and 95% confidence interval.
- Reason for terminating treatment, providing the frequency distribution of the patients according to the reason for terminating the treatment:
  - Unacceptable toxicity
  - Progression
  - o Death
  - o Other
- Time to Treatment Failure (TTF). TTF will be studied by means of a Kaplan Meier survival analysis, calculated as the time elapsed from the start of treatment with a tyrosine kinase inhibitor to tumour progression, treatment discontinuation for any reason or death from any cause.

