- Progression-Free Survival (PFS) Progression-free survival will be studied by means of a Kaplan Meier survival analysis, calculated as the time elapsed from the date of the start of treatment with a tyrosine kinase inhibitor to the date of progression/death, if the event occurs, or else it will be censored on the date of

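### PFS is censored at last follow-up, not at the last tumour assessment, so contact time without imaging counts as progression-free and median PFS can be overstated

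*SAP*

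**What the plan says.** The PFS event is "the date of the first documentation of objective tumour progression or death from any cause" (SAP 6, Treatment), with progression judged by RECIST 1.1 (SAP 6.1).

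For patients without an event, SAP 6.1 states that they "will be censored on the date of the last available follow-up". The PFS bullet in SAP 8.2.4 agrees: "or else it will be censored on the date of" the last follow-up of the patient. Neither document defines last follow-up. SAP 8.2.4 uses the same term for time on treatment, which suggests a general contact date.

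On imaging, Protocol 7.2 describes the month 3 visit as "coinciding with the first control CT according to routine clinical practice" and names further CTs at months 6 and 9. No later CT is named. Protocol 8.5 says "no additional tests are to be performed as part of the study". Protocol 7.9 lists as a limitation that "PFS will be evaluated by each investigator in line with routine clinical practice with no centralised evaluation".

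The lead-in to SAP 8.2.4 says that efficacy is studied "on completion of the firstline treatment or else on the date of the patient's last follow-up when the cut-off is decided".

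**The concern.** Tumour progression is established by imaging. A visit, a questionnaire or a safety contact without a scan cannot show that a patient is progression-free, yet the rule credits the time up to that contact as progression-free.

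The plan leaves room for such time. Questionnaires are completed each cycle and extra visits may occur (Protocol 7.1). Safety observation runs at least 28 days past the last dose, and drug-related events are followed until resolved or stable (Protocol 9). Data collection can run to about 27 months, while CTs are named only to month 9. The patients most exposed are those who stop for toxicity, because contact may go on after their scans become less regular.

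At stake is median PFS, a named secondary objective. Readers may compare it with the 11 and 9.2 months cited in the protocol's background.

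**Working it through.** **Plan's own figure.** There is none to reproduce. The documents give no expected PFS median, event count or precision for this study. N = 100 is linked only to the percentage with fatigue.

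**Inputs from the documents.** Median PFS 11 months (sunitinib) and 9.2 months (pazopanib), and toxicity discontinuation of 19% and 8% on sunitinib (Protocol 5). Recruitment February 2016 to August 2017 with data collection to May 2018 (Protocol 3), so follow-up of 27 months for the first patient and 9 for the last.

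**Assumptions not in the documents.** Exponential times to progression and to toxicity stop, independent of each other; uniform accrual; background stopping rates apply to this cohort. Here f is the share who would stop for toxicity before progression if there were no cut-off. With the cut-off, f = 19% means that about 14% actually stop.

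**Step 1: closed form, no scan grid, deaths ignored.** Let λ = ln 2 / median. If stoppers are never scanned again but are followed to cut-off, Kaplan-Meier under the SAP rule estimates

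1 − (1 − f)(1 − exp(−λt/(1 − f))).

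Setting this to 0.5 gives t = −ln(1 − 0.5/(1 − f)) × (1 − f)/λ. For a true median of 11, λ = 0.06301:

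- f = 0.19: −ln(1 − 0.6173) = 0.9605; 0.9605 × 0.81/0.06301 = 12.35 months (+1.35, +12%).
- f = 0.08: −ln(1 − 0.5435) = 0.7841; 0.7841 × 0.92/0.06301 = 11.45 months (+0.45, +4%).

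For a true median of 9.2 the same formula gives 10.33 and 9.57. Censoring at the last assessment returns the assumed median.

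**Step 2: length of unscanned follow-up** (simulation; true median 11, f = 19%, deaths ignored). Zero gives 11.0; 28 days, 11.15; 3 months, 11.5; 6 months, 11.9; to cut-off, 12.4. Counting deaths as events, with an assumed median of 12 months from progression to death, lowers the last figure to 12.0.

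**Step 3: with scans** (simulation; every 2.5 to 3.5 months, deaths counted, assumed median 15 months from progression to death, constant stopping hazard). Estimated median PFS in months:

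| True median | Stoppers | Scanning and follow-up after the stop | Last follow-up | Last scan |
|---|---|---|---|---|
| 11 | – | complete scanning | 12.3 | 12.1 |
| 11 | 8% | unscanned, to cut-off | about 12.6 | 12.0 |
| 11 | 19% | unscanned, 28 days | 12.2 | 11.9 |
| 11 | 19% | unscanned, to cut-off | 13.3 | 11.9 |
| 9.2 | – | complete scanning | 11.0 | 10.0 |
| 9.2 | 19% | unscanned, to cut-off | 11.8 | 9.7 |

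Repeat runs gave 12.5 to 12.7 for the 8% row and 12.8 to 13.3 for the 19% row followed to cut-off. Even complete scanning gives values above the true median, because progression is dated at the scan that finds it. With a true median of 9.2 the curve crosses one half on a nearly flat stretch between scans, so a small vertical shift moves the median by about a month.

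**Step 4: 12-month PFS** (3-month scan grid, true median 11, f = 19%, deaths ignored). With scanning continued it is 0.505 under last-assessment and about 0.515 under last-follow-up censoring. When scans cease at the stop, last-follow-up censoring gives 0.514 (28 days) to 0.548 (to cut-off), and last-assessment censoring about 0.49.

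**Step 5: against sampling error.** At N = 100 the simulated SD of the median is about 1.4 months (true median 9.2) to 1.7 (true median 11). The excess due to stoppers in Step 3 is 13.3 − 12.3 = 1.0 month, or 1.0/1.7 ≈ 0.6 SD. In Step 1 it is 1.35/1.7 ≈ 0.8 SD.

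**The case against.** The strongest reply is that nothing in the documents says scanning ends when a patient stops for toxicity, or that such a patient is followed to cut-off. CTs follow routine practice, and the protocol only rules out added tests. The last scheduled questionnaire is at month 9 or at discontinuation, and the only stated minimum after the last dose is the 28-day safety period. With 28 days of unscanned follow-up the inflation disappears (12.2 against 12.3 months). This stands, and it makes the bias conditional.

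A reader might also infer a conflict between the lead-in of SAP 8.2.4, which can be read as ending efficacy follow-up at the end of first-line treatment, and the censoring rule. The documents do not support that strongly. The PFS bullet in 8.2.4 carries its own rule and it matches 6.1. PFS ends only at progression or death, while discontinuation is counted separately in TTF. What is missing is a definition of last follow-up.

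Two further points stand. The replacement rule is not free of bias: it can run slightly low and does not correct for stopping that is related to prognosis. And PFS is a secondary endpoint of a descriptive study, with investigator assessment already declared as a limitation.

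None of this removes the mismatch between an imaging-based event and a contact-based censoring date.

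**Conclusion.** The concern holds in a conditional form. The censoring date is not tied to a tumour assessment, so contact time without imaging counts as progression-free and median PFS can be overstated.

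Under the Step 3 assumptions with a true median of 11 months, the estimate goes from about 12.3 months with complete scanning to about 12.6 to 13.3 when 8% to 19% stop, are unscanned and are followed to cut-off. Last-scan censoring gives about 12. The excess due to stoppers is near zero if unscanned follow-up is short or scans continue. With a true median of 9.2 months, the choice of rule alone moves the median by about 1 month.

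A reader might go further and conclude that median PFS will be overstated because toxicity stoppers are no longer scanned. The documents do not say that. Nor do they support an inflated median above 14 months. Such values need further assumptions: all stops in months 0 to 6 gave about 14.4, and a rigid 3-month grid with deaths not counted gave 14.6. The documents give no timing of stops, and the SAP does count deaths.

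The primary FACIT-Fatigue analysis and N = 100 are unaffected. This is a cheap improvement of minor to moderate severity.

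**What to change.** In SAP 6.1 and 8.2.4, replace the censoring sentence with: *Patients without progression or death are censored at the last evaluable tumour assessment, or at treatment start if there is none.* In addition:

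- State that progression continues to be collected after drug stop until second-line treatment or data cut-off, and say how missed scans are handled.
- Record the date of the last tumour assessment. The variable lists name the progression date but no scan dates; test results are source documents (Protocol 7.4). No extra scan is needed.
- Keep last-follow-up censoring as a sensitivity analysis and report both medians.

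The cost is SAP wording and one date per patient from source records. The main median will probably be slightly less favourable and may run slightly low. Reporting both rules shows the reader how much depends on the choice.

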#### 6.2 SAFETY OBJECTIVES

- **Safety:** the safety of the tyrosine kinase inhibitor will be evaluated by describing the incidence of serious adverse events, the side effects included in the potential drug risk management plan and all CTCAE grades if fatigue and/or hand-foot syndrome are present.

#### 7 HANDLING OF MISSING DATA

No criterion for replacing missing values will be used.

#### 8 STATISTICAL ANALYSIS AND METHODOLOGY

#### 8.1 STATISTICAL METHODS

The investigator will collect data from the enrolled patients in an electronic Case Report Form specially designed for this study.

The patient number we provide is a serial number devoid of any identifying value.

The information is stored in an Access database, which in turn is associated with a file, "WorkGroup", detailing the user code and permits of the investigator within the database. People not within this working group cannot access the database.

A Data Management Plan (DMP) will be developed and once approved by the person responsible for the study, the "Queries" will be programmed in the electronic case form so that when the investigator saves the data, it informs him/her of any doubts regarding the data.

All changes made by the investigators during the collection of data will be stored in a table specially designed for this purpose, indicating the user, date, modified field, the old value and the new value.

The fatigue-related quality of life of the patients and the quality of life of patients with palmar-plantar erythrodysaesthesia (hand-foot syndrome) will be studied using the mean, standard deviation and confidence intervals if they follow normal distribution, or the median, minimum, maximum and interquartile range if they do not follow Gaussian distribution. The Wilcoxon test will be used to analyse the inter-visit correlation for patients' quality of life.

The objective response rate according to RECIST version 1.1 will be studied using absolute and relative frequencies.

In order to study the impact of drug administration time, napping, temporary interruptions and dose reductions on fatigue and hand-foot syndrome control, independent samples will be compared using Pearson's chi-square test (or Fisher's exact test for 2x2 tables or likelihood ratio test for mxm tables, if necessary) in the case of qualitative variables and Student's t-test, one-way ANOVA test or non-parametric equivalents, such as the Mann-Whitney U test or Kruskal-Wallis H test in the case of quantitative variables.

The Kaplan-Meier survival estimate will be used to study both the PFS and TTF of patients. The log-rank test will be used to compare the survival distributions.

The assumptions of normality and homoscedasticity of the variables will be studied for the use of parametric tests. Estimates will be calculated with a 95% confidence level and the SPSS statistical analysis software package, V19.0 or later, will be used.

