3.1.2. Exclusion Criteria

Patients must not meet any of the exclusion criteria described below.

1) Patients who are not candidates for first-line treatment with a tyrosine kinase inhibitor.

2) Patients who are receiving the treatment as second-line or subsequent therapy.

3) Untreated hypothyroidism.

4) Untreated severe anaemia.

5) Pregnancy or breast-feeding.

6) Myocardial infarction or cerebrovascular accidents (CVA) within the last 6 months.

7) Severe hepatic impairment.

8) Concomitant use of potent inhibitors or inducers that interact with hepatic cytochrome CYP3A4.

QUALITY OF LIFE:

 Fatigue-related quality of life of patients evaluated using the validated 13-item FACIT-Fatigue scale for patients with kidney cancer in Spanish. Company FACIT.ORG (USA) (ANNEX 8). Quality of life in patients with palmar-plantar erythrodysaesthesia (hand-foot syndrome). To be evaluated according to CTCAE Version 4.0 Published: May 28, 2009 (v4.03: June 14, 2010) with scores running from 1 to 3 (see ANNEX 9).

SCHEDULE

Date of submission to AEMPS for classification: October 2015

Proposed date of submission to the IEC: November 2015

Proposed date of inclusion of the first patient in the study: February 2016

Proposed end-of-recruitment date: August 2017 or after recruiting 100 patients, whichever occurs first.

Recruitment period: 18 months.

Proposed date of the end of data collection: May 2018 or whenever the last patient passes to the 2nd line of treatment, whichever occurs first.

Expected date of Interim study report: After completing the 9 months of fatigue-related quality of life follow-up in all patients, estimated July 2018.

Expected date of Final study report: October 2018

SOURCE OF FUNDING

Pfizer SLU, as sponsor of the study, will provide financial compensation to the participating sites/investigators. Such compensation will be explicit and transparent, without prejudice to the internal rules of their employing agencies and in accordance with specific regulations in the ARs and at the sites where the study is conducted.

Fees are to fund the collection and transcription of clinical and epidemiological data from patients and the quality of life questionnaires to the case report forms.

AMENDMENTS AND UPDATES

None

Amendment No.	Date	Substantial or administrative amendment	Amended protocol section(s)	Summary of change(s)	Reason

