7. METHODS OF INVESTIGATION

7.1. Study design

Prospective, multicentre, observational, post-authorisation study in patients aged ≥ 18 years diagnosed with metastatic renal cell carcinoma who are to be given a tyrosine kinase inhibitor as first-line treatment.

The study will evaluate measures to improve patients' quality of life, such as time of drug administration, napping, temporary treatment breaks and dose reductions.

Fatigue-related quality of life will be evaluated using the Spanish version of the *FACIT*–Fatigue **Questionnaire**, which will be completed by the patient individually after having been explained by the clinician or a person appointed by the investigator (nursing staff, clinical trial coordinator)

in the treatment room or another room during the scheduled visits, once the patient understands how to complete the form.

The FACIT–Fatigue questionnaire will be handed out together with the patient diary at the following treatment times, which coincide with the visits, according to the department's protocol:

- 1) **Baseline** (before starting the treatment)
- 2) Month 3
- 3) Month 6
- 4) Month 9 or upon treatment discontinuation
- 5) Additional visits according to the oncology department's clinical practice: additional visits may be recorded on the case report form (e.g. at 15 days)

The patient will also complete this FACIT-Fatigue questionnaire at home **at the start of each cycle** (for sorafenib and pazopanib a cycle will be 6 weeks of treatment), even if this does not coincide with scheduled visits to the hospital.

The hand-foot syndrome-related quality of life evaluation that patients may be asked to take part in will be performed on the basis of the CTCAE V4.03 2010 with scores running from 1 to 3 (see ANNEX 9).

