#### 2.1 STUDY DESIGN

Prospective, multicentre, observational, post-authorisation study in patients aged  $\geq 18$  years diagnosed with metastatic renal cell carcinoma who are to be given a tyrosine kinase inhibitor as first-line treatment.

The study will evaluate measures to improve patients' quality of life, such as time of drug administration, napping, temporary treatment breaks and dose reductions.

Fatigue-related quality of life will be evaluated using the *Spanish version of the FACIT– Fatigue Questionnaire (see ANNEX 1)* which will be completed by the patient individually after it has been explained to them by the clinician or a person appointed by the investigator (nursing staff, clinical trials coordinator) in the treatment room during the scheduled visits, once the patient understands how to complete the form.

The FACIT–Fatigue questionnaire will be handed out at the following treatment times, which coincide with the visits, according to the site's protocol:

- 1) **Baseline** (before starting the treatment)
- 2) Month 3
- 3) Month 6
- 4) Month 9 or upon treatment discontinuation
- 5) Additional visits according to the oncology department's clinical practice: additional visits may be recorded on the case report form

The patient will also complete this FACIT-Fatigue questionnaire at home **at the start of each cycle** (for sorafenib and pazopanib a cycle will be 6 weeks of treatment), even if this does not coincide with scheduled visits to the hospital.

The hand-foot syndrome-related quality of life evaluation that patients may be asked to take part in will be performed on the basis of the CTCAE V4.03 2010 with scores running from 1 to 3 (see ANNEX 2).

The study will start at each site after the contract has been signed by all parties and all documentation and information on the procedures and objectives of the study have been received by the person appointed by the sponsor. Recruitment will be competitive between all the participating sites (estimating between 1 and 4 patients per site) and will finish once 100 patients have been recruited.

The investigator will be guided by routine clinical practice at all times when making decisions regarding the best available treatment option for the patient.

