#### SECONDARY OBJECTIVES

- 1) Quality of life in patients with palmar-plantar erythrodysaesthesia (hand-foot syndrome).
- 2) To assess the following adverse events according to version 4 of the CTCAE (Common Terminology Criteria for Adverse Events): any grade of fatigue and HFS.
- 3) To study what role aerobic exercise (walking quickly, running, swimming, playing tennis, dancing and/or riding a bike) plays in the onset of fatigue before starting and during treatment.
- 4) To evaluate what impact the time of day of drug administration, napping, temporary treatment breaks and dose reductions have on controlling fatigue and hand-foot syndrome.
- 5) Time to Treatment Failure (TTF), defined as the time from the start of treatment with a tyrosine kinase inhibitor to tumour progression, treatment discontinuation for any reason or death from any cause.
- 6) Progression-Free Survival (PFS) (median): time from the start of treatment with a tyrosine kinase inhibitor to tumour progression or death from any cause.
- 7) Objective Response Rate according to RECIST version 1.1.

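### Hand-foot syndrome quality of life is measured only by the CTCAE grade in affected patients, so secondary objective 1 repeats objective 2 and its score-type summary does not suit the variable

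*SAP*

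**What the plan says.** The protocol title and secondary objective 1 (protocol section 6, SAP section 2.2) name quality of life in patients with HFS. Secondary objective 2 separately covers CTCAE v4 adverse effects, namely "any grade of fatigue and HFS".

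The measurement of objective 1 is described in several places, always in the same way:

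- Protocol section 3 (Abstract, under Quality of life): "To be evaluated according to CTCAE Version 4.0", with scores 1 to 3.
- Protocol section 7.1: "The hand-foot syndrome-related quality of life evaluation that patients may be asked to take part in will be performed on the basis of" the CTCAE, again scored 1 to 3. SAP section 2.1 agrees: "performed on the basis of the CTCAE V4.03 2010 with scores running from 1 to 3".
- SAP section 6 defines the variable "in cases in which HFS is present with a score from 1 to 3 according to version 4 of the CTCAE". Protocol section 7.3 has the same definition.

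The annex headed as HFS quality of life (protocol Annex 9, SAP Annex 2) is an extract of the CTCAE skin-disorder table.

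For analysis, SAP section 8.1 (and protocol section 7.7) treats HFS quality of life in one sentence with fatigue-related quality of life: "the quality of life of patients with palmar-plantar erythrodysaesthesia (hand-foot syndrome) will be studied using the mean, standard deviation" and confidence intervals under normality, otherwise median, minimum, maximum and interquartile range. The next sentence applies the Wilcoxon test between visits to patients' quality of life. SAP section 8.2.3 treats HFS differently: frequency of any grade, distribution over grades 1 to 3 among cases, and paired sign or McNemar tests.

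**The concern.** A toxicity grade is not a quality-of-life measurement, and here the two share one variable. Objective 1 would therefore either go unreported or appear as objective 2 under another name. The report could then claim a finding on HFS quality of life for which no patient-reported data exist.

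The summary in SAP section 8.1 adds a second problem. It handles a three-level ordinal grade like the 0 to 52 FACIT-Fatigue score. Because the grade exists only for patients with HFS, its centre depends on who currently counts as a case. New mild cases pull it down and resolving mild cases push it up, whatever happens to the patients as a group. A paired test on the same variable could use only patients with HFS at both visits, so onset and resolution would drop out.

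**Working it through.** The point rests on no planned figure, so there is none to reproduce. The check is of the text, followed by small illustrations with assumed counts.

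**1. Is there any other measure of HFS quality of life?**

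| Candidate | What the documents show |
|---|---|
| HFS annex | CTCAE rows, including unrelated ones such as hypertrichosis and nail loss; not a questionnaire |
| FACIT-Fatigue | 13 items on fatigue, energy and activity; none on hands or feet |
| Patient diary (SAP 8.2.3) | Napping, exercise, time of medication |
| FACIT-Fatigue by HFS status | No such analysis in SAP 8.2.3 or the table list in SAP 9 |
| HFS quality-of-life table | None in SAP 9; HFS tables cover presence and associations, and the quality-of-life table is FACIT-Fatigue |

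Objectives 1 and 2 therefore use one variable for HFS.

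**2. Which branch of SAP 8.1 applies?** The SAP does not name a normality test; Shapiro-Wilk at 5% is assumed. Scores of 1, 2 and 3 were simulated with assumed grade mixes (%) of 50/35/15, 40/40/20, 25/50/25 and 60/30/10, at 20, 30 and 50 cases, with 3,000 runs each. Normality was rejected in 100% of runs in all 12 settings. With 20 or more cases the rule would almost certainly lead to the median and interquartile range. Fewer than 20 cases were not examined.

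**3. Does the cases-only summary track the burden of HFS?** Counts are assumed.

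*Mild cases appear (100 patients).* At first there are 10 cases, all grade 3:

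- mean = 3.0, median = 3, affected = 10/100 = 10%.

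Then 30 grade 1 cases are added:

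- mean = (10×3 + 30×1)/40 = 60/40 = 1.5
- median of 40 values, 30 of them grade 1, = 1
- affected = 40/100 = 40%.

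Both summaries fall, although nobody improved.

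*Mild cases resolve.* Grades 1/2/3 in 15/10/5 patients:

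- mean = (15×1 + 10×2 + 5×3)/30 = 50/30 = 1.67
- median (15th and 16th values are 1 and 2) = 1.5.

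All 15 grade 1 cases resolve and the others stay as they were:

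- mean among remaining cases = (10×2 + 5×3)/15 = 35/15 = 2.33
- median among remaining cases = 2.

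Both rise, although nobody worsened. With the resolved patients coded 0, the mean is 35/30 = 1.17, a fall of 0.5.

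**4. Does the mean describe the grades?** A mean of 2.0 arises from 30 patients all at grade 2 (SD 0), from 15 at grade 1 and 15 at grade 3 (SD 1.02), or from 10/10/10 (SD 0.83). The median is 2 in all three.

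**5. Do the two SAP sections agree?** Section 8.1 gives a centre and spread with Wilcoxon. Section 8.2.3 gives frequencies by grade with sign or McNemar tests. For the same HFS grade these are different analyses, and the SAP does not say which one reports objective 1.

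**The case against.** The other side has good points.

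- **Mean and SD are conditional.** A reader might infer that the plan will report a mean grade whatever the data look like. The documents do not support that: section 8.1 switches to the median when normality fails, and step 2 suggests that it would.
- **The frequencies are already planned.** A reader might also infer that a rise from 10% to 40% affected would go unseen. It would not. Section 8.2.3 and the HFS presence table in section 9 give the any-grade frequency at months 3, 6 and 9. Patients without HFS are its complement.
- **The definition is open.** Both documents say plainly that the variable is the CTCAE grade. Grades 2 and 3 are defined partly by pain and by limits on daily activities, so the grade carries some functional information. The objective as defined can be reported.
- **The wording in protocol section 7.1 about patients being asked to take part** might suggest a separate patient questionnaire. The same sentence names the CTCAE as its basis.

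The first two points limit the harm but leave the fault in place. The median moves in the same misleading direction as the mean in both examples, and correct frequencies in section 8.2.3 are a reason to remove the competing summary. The third point makes the grade a weak proxy for functional impact. It does not make it a patient-reported quality-of-life result, and it adds nothing to objective 2.

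**Conclusion.** Wrong as written, minor in size. Secondary objective 1 is a mislabelled endpoint: what is recorded is HFS severity among cases, which is the HFS part of objective 2. The data can describe how often HFS occurs and how severe it is. They cannot show how HFS affects quality of life beyond what the grade definitions contain.

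The summary in SAP section 8.1, whichever branch applies, is unsuitable for an ordinal grade scored only in cases, and it is inconsistent with section 8.2.3. The examples show the direction of the distortion. Their counts are assumed and do not predict what the study will find.

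A reader might infer that the HFS results as a whole, or the study's main conclusion, are compromised. The documents do not support that. Most of the correct HFS frequencies are already planned, and the primary FACIT-Fatigue objective does not depend on this variable.

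The conclusion assumes that the case report form holds no separate HFS questionnaire. The form was not available for this check, but neither variable list mentions one.

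**What to change.** 1. Reword secondary objective 1 and the variable in SAP section 6 and protocol section 7.3 as 'severity of hand-foot syndrome (CTCAE v4 grade)'. Add the same caveat to the study title and to the heading of protocol Annex 9 and SAP Annex 2.
2. Remove HFS from the mean/median sentence in SAP section 8.1 and protocol section 7.7, and limit the Wilcoxon quality-of-life sentence to FACIT-Fatigue.
3. Extend the HFS table in SAP section 8.2.3 to grades 0 to 3, with 0 meaning no HFS, among all treated patients assessed at each visit. Give the denominator and 95% confidence intervals. The severity table in protocol section 9.1 already allows a grade 0. For scale, a 10% proportion in 100 patients has a half-width of 1.96×√(0.10×0.90/100) = 5.9 percentage points.
4. Optionally, describe FACIT-Fatigue by HFS grade, labelled as fatigue-related only.
5. State in the SAP and the report that HFS-specific quality of life was not measured.

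The cost is wording in both documents and one table definition, with no new instrument, visit or patient. The downside is that the sponsor gives up the HFS quality-of-life claim.
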